## 4.2 Study Regimen

This prospective, multicenter, cohort study will assess ribociclib pharmacokinetics and pharmacogenomics in female patients with HR+/HER2- metastatic breast cancer. Potential trial patients will be pre-identified at participating centers.

Patients who have adequate hematologic, hepatic, and renal function will be screened for enrollment. Patients who ultimately meet the inclusion and exclusion criteria as detailed in Section 3, and desire participation, will be enrolled.

## 4.3 Patient Screening, Enrollment, Monitoring

The screening and monitoring procedures include the following listed below. Details are provided in [Table 14](#).

#### **4.3.1 Informed Consent**

Signed informed consent will be obtained from the patient before any study-specific procedures are undertaken. Additionally, patient will receive COVID-19 related documentation per IRB and Georgetown university policy.

#### **4.3.2 Medical History**

The following information should be collected during the screening period:

1. Complete medical history, including documentation of any clinically significant medical conditions
2. Performance status (ECOG)
3. Medication information, including over the counter medications and herbal supplements
4. Smoking history will be documented
5. Presence and severity of any symptoms/conditions associated with their advanced solid tumor malignancy
6. Detailed oncology history, including:
  - a) Primary tumor: date of diagnosis, histology/cytology, and location
  - b) Metastasis information: date of diagnosis, histology/cytology, and location
  - c) Surgical history
  - d) Anti-cancer and radiation treatments administered (including dates and type of modality, and if therapy was in the neoadjuvant, adjuvant, or metastatic setting)

#### **4.3.3 Demographics**

Age, sex, and self-reported race/ethnicity will be recorded.

#### **4.3.4 Patient Eligibility Criteria**

Inclusion and exclusion criteria (per section [3.2](#) and [3.2](#), respectively)

#### **4.3.5 Review Concomitant Medications**

Permitted, not recommended and prohibited concomitant medications, per section appendices [14.4](#) and [14.5](#).

#### **4.3.6 Physical Exam and Assessment of Performance Status**

At screening, a physical examination, height, weight, blood pressure, and pulse rate is required. Symptom-directed physical examinations, blood pressure, weight, and pulse rate will be performed. All physical examinations and vital signs assessments should be

performed by a physician or registered nurse or other qualified health care provider according to local regulations.

#### **4.3.7 CYP3A5 Phenotype Screening**

After informed consent is complete, participants will undergo CYP3A5 screening to ensure the necessary number of participants with each phenotype are enrolled. If sample size requirements (sections 3.3 and 9.1; at least 3 participants in AA or Black cohort who are CYP3A5 poor metabolizers; at least 3 participants in the NHW cohort who are CYP3A5 intermediate or normal metabolizers) are met, then CYP3A5 phenotype screening may be bypassed per Principal Investigator discretion.

A buccal sample will be collected from participants upon completion of informed consent. Upon collection, the sample and kit will be mailed to Kailos Genetics to perform targeted next-generation sequencing on CYP3A5. Samples will be processed in accordance with Clinical Laboratory Improvement Amendments (CLIA)-certified laboratory procedures. Similar to other pharmacogenetic results (PharmacoScan™ test discussed in section 4.3.8), these results will not be returned to the participant. The test results will be provided to the study team through a secure electronic method (e.g., encrypted email, Box.com).

Patients will be considered a screen failure if:

- The participant is a CYP3A5 poor metabolizer AND identifies as non-Hispanic White AND the study has already enrolled 15 participants who meet these criteria.  
OR
- 2) The participant is a CYP3A5 intermediate or normal metabolizer AND identifies as African American AND the study has already enrolled 15 participants who meet these criteria.

The standard turnaround time for CYP3A5 screening will be one week or less. The timing can be as quick as 48 hours if the participant's situation requires a faster turnaround time.

#### **4.3.8 Laboratory Samples**

Laboratory samples for this study will be assessed using the certified laboratory at the Investigators' institutions or at a clinical laboratory such as Quest or LabCorp and these data will be used for all data analysis. The Principal Investigator or sub-Investigator will review, initial, and date all laboratory results and electrocardiograms. Any laboratory value outside the reference range that is considered clinically significant by the Investigator will be followed as appropriate. Clinically significant laboratory values will be recorded as AEs if they meet the criteria as specified in Section 8.1.

Hematology samples (complete blood count [CBC]) will be collected and assessed using a certified laboratory. The Investigator will review, initial, and date all laboratory results. Any laboratory value outside the reference range stated in the inclusion criteria will

preclude the patient from study participation. Comprehensive metabolic panel (CMP) to include: albumin, alkaline phosphatase, ALT, AST, blood urea nitrogen (BUN), creatinine, electrolytes (sodium, potassium, calcium, chloride, bicarbonate), glucose, and total bilirubin. Any laboratory value outside the reference range stated in the inclusion criteria will preclude the patient from study participation. The CBC and CMP are performed per standard clinical practice and are not drawn specifically for research purposes.

Serial blood samples for pharmacokinetic and pharmacogenomic studies will be obtained during cycle one, between days 8 and 16 in the Georgetown University Clinical Research Unit, or locally at the enrolling site. Blood samples will be collected immediately prior to the ribociclib dose, and  $0.5\text{hr} \pm 5\text{min}$ ,  $1\text{hr} \pm 5\text{min}$ ,  $2\text{hr} \pm 15\text{min}$ ,  $4\text{hr} \pm 15\text{min}$ ,  $6\text{hr} \pm 15\text{min}$  after the daily dose of ribociclib. Samples will be collected in the Georgetown University Clinical Research Unit, or at the local site and shipped to the National Institute of Health to process and analyze the data.

Frozen whole blood will be used to isolate DNA via the Wizard® Genomic DNA Purification Kit (Promega). This assay is able to yield 250-500 $\mu\text{g}$  from 10mL of whole blood. The Tissue Culture and Biobanking Shared Resource (TCBSR) will perform DNA isolation in batches. Isolated DNA can then be used for pharmacogenomic testing.

Pharmacogenomic testing will be performed by the National Cancer Institute on the PharmacoScan™ microarray (Thermo Fischer). PharmacoScan™ analyzes 4,627 markers in 1,191 genes. These assay allows for the genotyping of multiple genes that have known pharmacogenetic value, including phase I and phase II enzymes, regulatory/modifier genes, drug target genes, and phase III/transporter genes. It includes 51 variants in *CYP3A4* and 22 in *CYP3A5*. In brief, the assay involves several steps, including amplifying DNA via multiplex polymerase chain reaction (PCR). The amplified DNA is then fragmented, precipitated, centrifuged and dried, and then resuspended and prepared for hybridization. Fragments then hybridize to the microarray and are processed by the GeneTitan™ Multi-Channel Instrument of PharmacoScan™.

Blood samples (3-4 mL for each timepoint) will also be used for serial pharmacokinetic studies. A liquid chromatography with tandem mass spectrometry (LC-MS/MS) method will be used to assess ribociclib concentrations in human plasma. An assay has been developed specifically for ribociclib (36). In brief, liquid chromatography separates compounds within, then an electrospray ionization and mass spectrometry are optimized to detect transitions between ribociclib and the internal standard [ $^{13}\text{C}_6$ ] ribociclib. LC-MS/MS consists of serial sampling (times mentioned above) that will allow for calculation of maximum concentration ( $C_{\text{max}}$ ), the time to reach  $C_{\text{max}}$  ( $T_{\text{max}}$ ), AUC, clearance, volume of distribution( $V_d$ ), elimination half-life, and mean residence time (MRT). The lower limit of quantitation is 0.5 nM of ribociclib in plasma. A backup blood sample will be obtained for each timepoint in the serial collection and for the pharmacogenetic test. A summary of the amount of blood collected from each patient is listed below:

- 10 mL – 1 sample (10 mL) for pharmacogenomics assay
- 10 mL – 1 backup sample (10 mL) for pharmacogenomics assay
- 18 mL – 6 samples (3 mL each) for serial PK

- 18 mL – 6 backup samples (3 mL each) for serial PK
- Total: 56 mL

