### **1.2.2 Pharmacokinetics**

According to the FDA label for ribociclib, repeated 600 mg once daily administration, steady-state was achieved after 8 days; the time to reach maximum concentration is between one and four hours after administration of ribociclib; the half-life of ribociclib is 32 hours (14).

The FDA label indicates clinical activity is primarily due to the parent drug and ribociclib is metabolized to other compounds that have a negligible contribution on clinical activity. The primary metabolic pathways of ribociclib include oxidation, N-acetylation, sulfation, cysteine conjugation, glycosylation, and glucuronidation (14). Ribociclib is the major circulating drug in plasma, accounting for 44%, however there is a possible contribution to ribociclib effect from circulating metabolites: M13 represents 22% of ribociclib exposure, M4 accounts for 20% and, M1 for 15% (14). Ribociclib is eliminated mainly via feces with a small contribution from the renal route (14).

Ribociclib undergoes hepatic metabolism mainly via CYP3A (14). Ritonavir is a strong CYP3A inhibitor, when ritonavir was given in combination with ribociclib there was an increase of the maximum concentration ( $C_{max}$ ) and the area-under-the-curve (AUC) of ribociclib increased by 1.7 and 3.2-fold, respectively (14, 15). Ribociclib in combination with erythromycin, a moderate CYP3A inhibitor, the  $C_{max}$  and AUC of the CDK 4/6 inhibitor increased by 1.3 and 1.9-fold, respectively (14). The opposite effect in ribociclib concentrations was noted with CYP3A inducers, such as rifampicin (14).

\* The magnitude of extrahepatic FMO1 contribution is unknown

James, A.D., et al. *Pharmacol Res Perspect.* (2020).

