### 2.2 Primary Endpoint

Ribociclib AUC (visit between days 8-16 of cycle 1) CYP3A5 poor metabolizers and CYP3A5 intermediate or normal metabolizers.

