## 2.4 Secondary Endpoints

1. Ribociclib pharmacokinetic properties: maximum concentration ( $C_{max}$ ), the time to reach  $C_{max}$  ( $T_{max}$ ), AUC, clearance, volume of distribution( $v_d$ ), elimination half-life, and mean residence time (MRT) at steady state (visit between days 8-16 of cycle 1).
2. Change in QTc interval between:
  - 1) baseline and between days 8-16 of cycle 1,
  - 2) baseline and scheduled visit prior to initiation of cycle 2
3. Laboratory abnormalities: neutropenia, ALT, and AST, between
  - 1) baseline and between days 8-16 of cycle 1,
  - 2) baseline and scheduled visit prior to initiation of cycle 2

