## **4 Study Design**

### **4.1 Study Design**

[figure not shown]
Two separate cohorts, based on self-identified race, will be followed prospectively during this study. Eighteen African Americans/Blacks and 18 Non-Hispanic White women with metastatic HR+/HER2- advanced breast cancer will be enrolled. Patients will receive ribociclib 600 mg oral (PO) daily for 21 consecutive days of 28-day cycles and endocrine

therapy with either letrozole or fulvestrant. Fulvestrant 500 mg intramuscular (IM) will be administered on days 1, 15, 29 of cycle one, and then monthly. Letrozole 2.5 mg oral daily continuously. If premenopausal women have not undergone bilateral salpingo-oophorectomy, they will receive a luteinizing hormone-releasing hormone (LHRH) agonist (e.g., goserelin leuprolide) for ovarian suppression in combination with fulvestrant or letrozole and ribociclib.

The Clinical Research Unit (CRU) is located in Georgetown University (7 East, Main Hospital, [name], Washington DC) and it provides specialized institutional resources in which clinical investigators can observe and study human physiology and treat diseases with innovative approaches. Subjects may have the visit between day 8 and day 16 of cycle 1 at the CRU or locally at the site.

Between days 8 and day 16 (i.e., steady state) of cycle 1 of ribociclib and fulvestrant, participants will provide serial blood samples at the Georgetown University Clinical Research Unit or locally at the enrolling site, immediately prior to the ribociclib dose, and 0.5hr ± 5min, 1hr ± 5min, 2hr ± 15min, 4hr ± 15min, 6hr ± 15min after the daily dose of ribociclib. Plasma samples will be analyzed at the National Cancer Institute via mass spectrometry to facilitate the measurement of pharmacokinetic properties. A blood sample will be utilized for pharmacogenetic testing on the PharmacogenoScan™ (ThermoFisher) microarray, which includes 51 variants in *CYP3A4* and 22 in *CYP3A5*.

Per FDA labeling, periodic electrocardiogram will be obtained prior to the first cycle, between C1D8-C1D16, at the start of the second cycle, and as clinically indicated. Additionally, a complete blood count (CBC) with differential and comprehensive metabolic panel (CMP) will be obtained at baseline (medical visit prior to C1D1), between C1D8-C1D16, at the start of the second cycle

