## 9.2 Statistical Analysis Plan

Primary analyses will be performed as follows. Within each race-based cohort, the ribociclib exposure which measured by ribociclib AUC will be summarized by median [Interquartile range, IQR], and two-sample t-test if normality holds or Wilcoxon-Mann-Whitney test will be used to compare AUC between CYP3A5 poor metabolizers and CYP3A5 intermediate or normal metabolizer in each independent race-based cohort. Secondary analyses will be performed as follows. Descriptive statistics will be used to characterize the data profile, frequency and percentages for categorical variables, and mean (SD) or median [IQR] for continuous variables based on the data normalization. Multiple regression will be used to identify variables associated with ribociclib AUC. To best account for any factor that may affect ribociclib exposure, covariates to be assessed include CYP3A5 metabolism status, renal function, liver function, age, race, weight, sex, among others. Any covariates with  $P < 0.2$  on univariate analysis will enter the stepwise multiple linear regression model, with  $P < 0.05$  considered statistically significant. This methodology will also be used to assess a change in absolute neutrophil count and QTc as the outcome variable. Depending on data distribution, a two-sample t-test or Wilcoxon-Mann-Whitney test will be used for 1) a change (baseline and C1D8-C1D16) in continuous variables (e.g., QTc, absolute neutrophil count) between CYP3A5 poor metabolizers and CYP3A5 intermediate or normal metabolizers, 2) to check the association between a continuous variables and categorical risk factors. Pearson correlation coefficient or Spearman correlation coefficient will be calculated to measure the association between two continuous variables. Fisher's exact test will be used for checking the association between two categorical variables. AEs will be assessed with descriptive statistics and univariate logistic regression will assess the occurrence of specific AEs with pharmacokinetic properties (e.g., AUC,  $C_{max}$ ). The approach from the linear regressions will be adapted to logistic regression to identify covariates associated with the occurrence of grade III or IV neutropenia.

Descriptive analysis of the PRO-CTCAE adverse event log to determine frequency of adverse events by race and by CYP3A5 genotype.

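### Do blood samples that stop at 6 hours leave AUC, half-life, residence time and volume of ribociclib without a usable basis?

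*Combined protocol and SAP*

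**What the plan says.** Section 2.2 defines the primary endpoint as "Ribociclib AUC (visit between days 8-16 of cycle 1", compared between CYP3A5 phenotype groups. Section 9.2 repeats the term without an interval: "the ribociclib exposure which measured by ribociclib AUC will be summarized by median". AUC0-24 appears once, in the Study Design row of the synopsis, as an example.

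On sampling, section 4.3.8 states "Blood samples will be collected immediately prior to the ribociclib dose", followed by post-dose draws. Section 4.1 gives the last of these as "6hr ± 15min after the daily dose of ribociclib". The blood-volume list in 4.3.8 counts six pharmacokinetic samples, so there is no 24 h draw.

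Section 4.3.8 then says that "LC-MS/MS consists of serial sampling (times mentioned above) that will allow for calculation of maximum concentration", and its list continues to volume, half-life and mean residence time. Section 2.4 makes these secondary endpoints: "elimination half-life, and mean residence time (MRT) at steady state (visit between days 8-16 of cycle 1".

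Section 1.2.2 supplies the relevant kinetics: "the half-life of ribociclib is 32 hours", and "the time to reach maximum concentration is between one and four hours after administration of ribociclib". It also puts steady state at 8 days of 600 mg once daily. Section 2.1 asks for steady-state pharmacokinetics, and section 5.3.1 sets once-daily dosing.

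**The concern.** The last sample is taken 6/32 = 0.19 of a half-life after the dose, and possibly only 2 h after the peak. A terminal slope cannot be read reliably from so short a stretch, yet section 4.3.8 says without qualification that half-life and the quantities resting on it can be calculated.

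The primary endpoint seems exposed too. If AUC means AUC0-24, most of it comes from hours with no sample. Sections 2.2 and 9.2 would allow three calculations: AUC0-6, AUC0-24 closed with the pre-dose value, or AUC0-24 extrapolated from the late post-dose slope. These differ in precision. With as few as 3 patients in the smaller phenotype group of each cohort (section 3.3), one badly extrapolated profile could move the comparison.

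**Working it through.** The documents state no figure for this point, so there is none to reproduce. The check uses their own kinetics and asks what the six samples can support.

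**Inputs from the documents.** Half-life 32 h and peak at 1-4 h (1.2.2); dosing interval 24 h (5.3.1); samples at 0, 0.5, 1, 2, 4 and 6 h (4.1, 4.3.8).

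**Assumptions not in the documents.** One compartment with first-order absorption, at steady state. Absorption rates ka of 4.442, 1.773, 0.997 and 0.644 per h place the peak at 1, 2, 3 and 4 h. Random lognormal error is 5% or 10% per sample.

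**Model.** k = ln 2/32 = 0.0217 per h. In units of bioavailable dose over volume,

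C(t) = ka/(ka − k) × [e^(−kt)/(1 − e^(−24k)) − e^(−ka·t)/(1 − e^(−24ka))], with AUC0-24 = 1/k = 46.2.

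**Step 1: unsampled share.** AUC0-6/AUC0-24 = 0.297, 0.292, 0.285 and 0.277 for peaks at 1 to 4 h. The unsampled part is 1 − 0.297 = 0.703 to 1 − 0.277 = 0.723, or 70-72%.

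**Step 2: the post-dose slope alone.** The true fall from 4 to 6 h is 4.2%, 4.2%, 3.6% and 1.9%, which is smaller than or similar to the sample error. With s = √ln(1 + CV²), the chance of a flat or rising 4-6 h slope is Φ(−ln(C4/C6)/(s√2)): 27-39% at 5% error and 38-45% at 10%. A three-point 2-6 h fit puts half-life between 16 and 64 h in only 16-62% or 23-35% of profiles. On this route the worry is justified.

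**Step 3: the pre-dose sample as the 24 h value.** At steady state on once-daily dosing, C(24) = C(0). The trapezoid through 0, 0.5, 1, 2, 4, 6 and 24 h, without error, gives 1.004-1.008 of the true AUC0-24. With error:

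| Quantity | 5% error | 10% error |
|---|---|---|
| log2 SD of AUC0-24, pre-dose closure | 0.04 | 0.08 |
| log2 SD of AUC0-24, three-point slope, rising slopes held flat | 0.11-0.17 | 0.23-0.29 |
| log2 SD of AUC0-24, three-point slope, not held flat | 0.19-0.22 | 0.39-0.45 |
| Half-life from 4, 6 and 24 h, 5th-95th percentile | 26-46 h | 22-70 h |
| Half-life within a factor of 2 | over 99% | 93-95% |

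Apparent clearance is dose/AUC0-24 and inherits the precision of the first row. Volume (clearance/k) is 0.80-1.43 of true at 5% error and 0.66-2.18 at 10%. Mean residence time is 36-66 h or 30-101 h against a true 46-48 h.

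**Step 4: is steady state reached?** Seven doses precede the day-8 dose, and 168/32 = 5.25 half-lives gives 1 − 2^(−5.25) = 97% of plateau, in line with section 1.2.2.

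**Step 5: which reading do the documents support?** The synopsis names AUC0-24, section 2.1 asks for steady-state kinetics, section 5.3.1 sets a 24 h interval, and a sample is drawn just before the dose. Together these indicate AUC over the dosing interval, closed with the pre-dose value or by a fitted model. No section suggests extrapolating from the 2-6 h slope.

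**The case for a change.** The strongest case for a change is that the choice is open, matters and costs nothing to settle. A true 2-fold difference in AUC0-24 (half-life 64 h against 32 h at equal volume, an assumption) would show as 1.85-1.92-fold in AUC0-6. Slope extrapolation would add a log2 SD of 0.11-0.45, against an effect of 1 on that scale. A rule fixed before the data are seen removes the choice. It remains true that sections 2.2 and 9.2 do not state one.

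But the harm depends on an analyst passing over the pre-dose sample and the synopsis in favour of a method that no section proposes. That is unlikely for the specialist group at the National Cancer Institute, which runs the assays and may receive covariates to assist the pharmacokinetic analysis (section 11.3).

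A second argument is that pre-dose closure is itself fragile. If poor metabolizers had a 64 h half-life and the others 32 h, a true 2-fold difference would appear as about 1.75 on day 8, 1.90 on day 12 and 1.95 on day 16. A missed previous dose gives about 0.71 of the true AUC0-24. A previous dose taken 16 h or 30 h earlier gives about 1.14 or 0.92. These limits are real, and the dosing log in Appendix 14.3 has no column for clock time. They arise, however, from the visit window and from adherence, and writing down the closure rule would not remove them. The diary, pill counts and adherence questionnaire let analysts identify missed doses.

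Method error should not be set against the 0.56 and 0.75 in section 9.1. The 0.56 is the SD of a fold change in a drug-interaction study and is not stated to be a between-patient SD of AUC.

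Half-life, residence time and volume are descriptive. Whether to label them imprecise or leave them out is a reporting preference, since intervals reported with them would show their precision.

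**Conclusion.** No change follows. The gap is real but is one of missing detail: the interval and the 6-24 h rule are unwritten in sections 2.2 and 9.2, while the rest of the protocol indicates steady-state AUC0-24 and supplies the sample needed to close it. On that reading AUC0-24 is recovered to within 1% before sample error, with an added log2 SD of 0.04-0.08, and clearance is equally sound. Half-life falls within a factor of 2 in 93% or more of profiles, so the statement in section 4.3.8 holds with limited precision.

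These sizes rest on a one-compartment model with a 32 h half-life, absorption rates chosen to match the stated peak times, 5-10% sample error, steady state, and a previous dose about 24 h earlier. A longer half-life in poor metabolizers or an irregular previous dose would weaken them. Neither would make the 2-6 h slope the better route.
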